In the recent years, the aim of IBD treatment has evolved from symptomatic control to deep remission, which is defined as the absence of symptoms, markers of inflammatory activity, and endoscopic lesions, and is associated with fewer admissions to hospital, surgeries and better HRQoL. Main current treatment modalities for UC and CD include 5-aminosalicylates, corticosteroids, immunomodulators (including thiopurines, methotrexate, tacrolimus, cyclosporine, and biological therapies), and surgery. Conventional treatment with corticosteroids and immunomodulators has not been able to reduce the complications of the disease or modify its course. Over the last decade, biologic treatments, such as infliximab, adalimumab, certolizumab pegol, golimumab and vedolizumab has been used in patients with moderate to severe CD, and in those with acute severe UC who failed to respond to corticosteroids.

At present, early introduction of immunomodulators and biologic agents in patients with more serious disease is probably the most widely accepted management strategy. Treatment of IBD with anti-TNF $\alpha$  since IBD diagnosis, albeit capable of inducing and maintaining mucosal healing and reducing surgery and hospitalization rates, may imply overtreatment of patients with milder forms of disease, thus emphasizing the need for accurate prognostic markers to guide patient selection. It is worth mentioning that although anti-TNF $\alpha$  therapy is thought to be an effective approach for IBD, up to 30% of patients do not respond to induction therapy (primary non-response) and a significant proportion loses response over time (secondary non-response). Very often patients profile in randomized controlled trials is quite restrictive and not representative of patients routinely treated under usual clinical conditions, especially, in terms of presence co-morbidities, concomitant treatments and previous use of biologics.

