- Urogenital manifestations of IBDComorbidities in UC and CD patients (defined as the coexistence of another medical condition alongside IBD, and does not imply causation) at the time of diagnosis and at the study visit, will be listed according to chosen according to the Charlson index:

Comorbidity Component	Score
Myocardial Infarction	1
Congestive Heart Failure	1
Peripheral Vascular Disease	1
Cerebrovascular Disease	1
Dementia	1
Chronic Obstructive Pulmonary Disease	1
Connective Tissue Disease	1
Peptic Ulcer Disease	1
Diabetes Mellitus	1 (mild), 2 (moderate- severe)
Moderate-Severe      Chronic      Kidney Disease	2
Hemiplegic	2
Leukemia	2
Malignant Lymphoma	2
Solid Tumor	2 (tumor), 6 (if metastasis)
Liver Disease	1 (mild), 3 (moderate-severe)
Acquired immunodeficiency syndrome (AIDS)	6

- Biological treatment/s for UC or CD followed during the reference period:
  - Starting date
  - Posology
  - Intensification of biological treatment: date and type of intensification
  - Continuing with the treatment
  - Date and reason for discontinuation, if applicable
  - New biological treatment prescribed after discontinuation, starting date, posology, continuing with the treatment, date and reason for discontinuation.
- Concomitant treatment with corticosteroids (e.g. prednisone, hydrocortisone, betamethasone, methylprednisolone, etc,) or immunosuppressives (e.g. Ciclosporin, Methotrexate, etc) during induction phase
  - Starting date, number of cycles

Other treatments followed before the reference period to be chosen from the following list:

- Aminosalicylates (e.g. mesalazine, Sulfasalazine, 5-ASA, etc), oral, enema, suppository.
- Corticosteroids (e.g. prednisone, hydrocortisone, betamethasone, methylprednisolone, etc), oral, enema, suppository.
- Thiopurines (e.g. azathioprine, mercaptopurine, etc).
- Immunosuppressives (e.g. Ciclosporin, Methotrexate, etc).
- Anti-diarrheal drugs.
- Pain medications.
- Antidepressants.
- Antibiotics.
- Use of alternative medicine (e.g. acupuncture, relaxation therapy, Qigong, herbal therapy, etc).
- Other (specify)

- Other treatments followed during the reference period to be chosen from the following list:
  - Aminosalicylates (e.g. mesalazine, Sulfasalazine, 5-ASA, etc), oral, enema, suppository.
  - Corticosteroids (e.g. prednisone, hydrocortisone, betamethasone, methylprednisolone, etc), oral, enema, suppository. Number of cycles
  - Thiopurines (e.g. azathioprine, mercaptopurine, etc).

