## 7. Statistical Analysis

### 7.1. Sample size calculation

Response to treatment with biologics is estimated at 50%, meaning that half of included patients are expected to be non-responders. Considering a minimal sample of 10 patients that present the event of interest per independent variable included in the logistic regression model and a maximum of 10 independent variables per model, a minimum estimated sample of 200 UC patients and 200 CD patients is required.

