#### **7.4. Assessment of the primary objective: Evaluate the impact of the co-morbidities profile in IBD patients on treatment response to biological therapy**

In order to determine the level of correlation between the co-morbidities profile and treatment response, adjusting for sociodemographic and clinical profile of patients, two logistic regression models will be conducted. The dependent variable of the models will be the lack of response during the induction phase (primary non response) and the loss of response during the maintenance phase (secondary loss of response) (see section 6.4.6). In both models independent variables will include all comorbidities included in the study, as well as sociodemographic and clinical variables as covariates. The maximum number of independent variables included in the model will be defined according to the number of patients per response category in the dependent variable. The maximum number of variables will be defined to ensure a minimum of 10 patients per independent variable and response category in the dependent one.

Depending on the volume of patients that have discontinued a biological treatment and started treatment with a different biologic during the reference period, this sample may be separately analyzed.

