7.2. Primary efficacy endpoint

- **Primary endpoint:** Evaluate the impact of the co-morbidities profile in IBD patients on treatment response to biological therapy.

The analysis that will be performed to answer the objective will be the following:

In order to determine the level of correlation between the co-morbidities profile and treatment response, adjusting for sociodemographic and clinical profile of patients, two logistic regression models will be conducted. The dependent variable of the models will be the **lack of response during the induction phase and the loss of response during the maintenance phase**. In both models independent variables will include all comorbidities, as well as sociodemographic and clinical variables as covariates.

- The following potential variables will be considered for the analysis:
 - Crohn's Disease or Ulcerative Colitis.
 - Myocardial Infarction (yes/no).
 - Congestive Heart Failure (yes/no).
 - Peripheral Vascular Disease (yes/no).
 - Cerebrovascular Disease (yes/no).
 - Dementia (yes/no).
 - Chronic Obstructive Pulmonary Disease (yes/no).
 - Connective Tissue Disease (yes/no).
 - Peptic Ulcer Disease (yes/no).
 - Mild Chronic Hepatopathy (yes/no).
 - Diabetes Mellitus (yes/no).
 - Hemiplegic (yes/no).
 - Moderate-Severe Chronic Kidney Disease (yes/no).
 - Diabetes with lesions in target organs (yes/no).
 - Solid Tumor (yes/no).
 - Leukemia (yes/no).
 - Lymphoma (yes/no).

- Moderate-Severe Chronic Hepatopathy (yes/no).
 - Solid tumor with metastases (yes/no)
 - Acquired immunodeficiency syndrome (AIDS) (yes/no).
 - Gender.
 - Race (caucasian, asiatic, latin, black, other).
 - Level of education (uneducated, primary education, secondary education, university education).
 - Working status (student, self-employed, employed by other, retired, housework, unemployed, temporarily unable to work, permanently unable to work, other).
 - Smoking habits (non-smoker, ex-smoker and smoker).
 - Alcohol abuse (yes/no).
 - Time from diagnostic of disease.
 - Disease location.
 - Discontinuation the biological treatment (yes/no)
- Each one of the variables will be compared between the subjects with primary non-response vs primary response and primary response maintenance vs loss of response and those variables whose p-value is lower than 0.1 are considered potential variables for performing a logistic regression analysis.

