 - For the comparison of the variables between subjects, the following criteria will be considered: dichotomous or categorical variables will be compared between the two groups using the Chi-squared test. Continuous variables will be compared between the two groups using the Student's T-test for independent samples.
- The logistic regression models will be assessed and the results will be submitted for any statistically significant model, providing the following results: Odds Ratio, 95%CI, p-value, sensitivity and specificity. The models will be assessed using stepwise automatic variable Wald entry (backward and forward) techniques and entry also assessing the specificity and sensitivity of the final model.

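### SAP 7.2 promises primary models containing all comorbidities, then lets p-values decide which comorbidities enter and which models are reported

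*SAP*

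**What the plan says.** SAP 7.2 first fixes the content of the two primary models, one for primary non-response and one for loss of response: "In both models independent variables will include all comorbidities, as well as sociodemographic and clinical variables as covariates". It then lists 29 potential variables: disease type, 19 comorbidities and 9 others. Each is compared between response groups, and "those variables whose p-value is lower than 0.1 are considered potential variables for performing a logistic regression analysis". Next comes automatic selection: "The models will be assessed using stepwise automatic variable Wald entry (backward and forward) techniques". No entry or removal level is given. On reporting, "results will be submitted for any statistically significant model".

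In SAP Appendix 1, tables 14.3.1.2 and 14.3.1.4 list both regressions with no significance condition.

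Protocol 7.4 also asks for all comorbidities, but limits the model by count: "The maximum number of variables will be defined to ensure a minimum of 10 patients per independent variable and response category in the dependent one". It mentions no screen, no stepwise step and no significance condition. Protocol 7.1 sizes each disease for "a maximum of 10 independent variables per model". The SAP repeats neither limit.

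**The concern.** The instructions in SAP 7.2 cannot all be followed. A model that contains every comorbidity is not one that contains only those passing p<0.1 and surviving stepwise removal. Two statisticians could each follow the section faithfully and fit different primary models.

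The choice affects the answer. The primary objective is the effect of the comorbidity profile on response, adjusted for patient characteristics. Selection on p-values can remove a comorbidity from the model meant to estimate its effect. Those that remain were kept partly because their estimates happened to be large, so their odds ratios are exaggerated. If the reporting condition is taken literally, a non-significant model yields no adjusted result and only the univariable comparisons remain.

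**Working it through.** **1. The plan's own figure.** Protocol 7.1 uses 10 events per variable, 10 variables and 50% non-response: 10 × 10 / 0.50 = 200 per disease. This reproduces the stated sample.

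**2. Terms needed.** SAP 7.2: 1 + 19 + 9 = 29 variables. Protocol 6.4.4 has 16 Charlson components. The SAP splits diabetes, liver disease and solid tumour by grade, so 16 + 3 = 19.

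**3. Terms allowed.** Capacity under protocol 7.4 is the smaller response category divided by 10, rounded down. The 50% is from protocol 7.1. The 30% is from protocol section 4: "up to 30% of patients do not respond to induction therapy (primary non-response". The 40% is for illustration.

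| Patients | Smaller category | Capacity |
|---|---|---|
| 400 pooled, 50% | 200 | 20 |
| 400 pooled, 40% | 160 | 16 |
| 400 pooled, 30% | 120 | 12 |
| 200 per disease, 50% | 100 | 10 |
| 200 per disease, 30% | 60 | 6 |

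With 400 patients:
- The 29 variables need 290 in the smaller category, which can hold at most 200. They never fit.
- The 19 comorbidities need 190, so a pooled event rate between 47.5% and 52.5% (190/400 = 0.475). At 50% one place is left for covariates.
- The 16 protocol components need 160, so a rate between 40% and 60%.
- At 30% events, 16 terms would need 160/0.3 = 534 patients and 19 would need 190/0.3 = 634.

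**4. Loss of response.** Protocol 6.4.5 defines it in initial responders. At 30% primary non-response, 400 × 0.7 = 280 remain and capacity is at most 140/10 = 14. SAP 7.1 does not state this restriction in its index-based definition. If it does not apply, the limits in the table hold instead.

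**5. What the screen does.** The documents give no comorbidity prevalence or effect size. Assume prevalence 6%, true odds ratio 2 and 30% events in 400 patients. The event risks are then 0.450 with the comorbidity (24 patients) and 0.290 without (376), a difference of 0.160.
- Null standard error: √(0.3 × 0.7 × (1/24 + 1/376)) = 0.0965
- Standard error under the alternative: √(0.450 × 0.550/24 + 0.290 × 0.710/376) = 0.104
- z for passing at two-sided p<0.1: (0.160 − 1.645 × 0.0965)/0.104 ≈ 0.01, so about 50% are excluded

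The same calculation with 280 patients and 28.6% events gives about 60%.

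**6. Simulation, same assumptions** (stepwise levels also assumed, because the SAP gives none):

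| Procedure | Excluded, n=400 / n=280 | Median odds ratio when kept |
|---|---|---|
| p<0.1 screen alone | 50% / 61% | about 2.7–2.8 / 3.1–3.2 |
| Screen, then backward removal at 0.10 | 53% / 63% | 2.8 / 3.4 |
| Screen, then backward or forward at 0.05 | 63% / 73% | 3.0 / 3.7 |
| Fixed model, this comorbidity forced in | 0% / 0% | 2.0 / 2.0 |

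Ranges for the screen alone (n=400 / n=280): odds ratio 2 at prevalence 3% to 10%, 66–35% / 72–47% excluded; prevalence 6% with odds ratio 1.5 to 3, 75–16% / 79–28%.

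**The case against.** Four points deserve weight.

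- **The study is exploratory.** Protocol 7.3 and SAP 5.1 call the analysis mainly descriptive, and no confirmatory hypothesis is set. True, but these odds ratios, intervals and p-values are still the planned answer to the primary objective. The label does not say which model to fit.
- **The list may be only a candidate pool.** SAP 7.2 does call the variables potential, and protocol 7.4 expects the data to limit the model. The sentence promising all comorbidities is then wrong and needs correcting. The missing stepwise levels and the reporting condition remain.
- **Prediction is a stated aim.** Protocol section 4 speaks of developing a comorbidity scale to predict response, and SAP 7.2 asks for sensitivity and specificity. Data-driven selection is common for that purpose. But the objective in both documents is impact, the SAP describes no building or validation of a scale, and prediction would not justify withholding a non-significant model.
- **Replacing the comorbidities by one summary term is a trade-off.** This stands. If a single comorbidity drives the effect (odds ratio 2, prevalence 3–10%), simulated power of a Charlson-like score is only 5–10%. If risk follows the score (odds ratio 1.2–1.5 per point), it is 40–95% at n=400 and 29–87% at n=280. A summary term would also conflict with protocol 7.4 as it stands.

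A reader might also infer more than the documents support. They do not show that the comorbidities can never fit: see the 47.5–52.5% and 40–60% ranges above. The 10 variables in protocol 7.1 are a sample-size assumption per disease, not a limit on a pooled model. Nor is pooling truly open: two models, disease type among the candidates and one regression table per outcome strongly imply it, so confirmation is enough. Finally, the unconditional tables in Appendix 1 mean that non-reporting is a risk of the wording, not a settled plan.

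**Conclusion.** The concern holds. SAP 7.2 contradicts itself on the content of both primary models. It adds p-value selection and a reporting condition absent from protocol 7.4, and it omits the one limit that protocol 7.4 sets.

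The contradiction rests on the text alone. The size of the harm rests on assumed prevalences, odds ratios, event rates and stepwise levels. Within those assumptions the screen excludes a real effect in anything from 16% to 79% of studies, about half in the central case, and exaggerates what passes. The figure of 280 patients for loss of response rests on protocol 6.4.5 and on 30% primary non-response.

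Because the primary analysis is not defined as written, this should be settled before database lock.

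**What to change.** In SAP 7.2:

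1. Delete the p<0.1 screen and the stepwise selection for the comorbidity terms. Pre-specify one model per outcome with comorbidity forced in and a fixed, ordered covariate list, cut off by the protocol 7.4 limit. Age is collected but missing from the SAP 7.2 list and should be considered.
2. Name in advance how comorbidity is represented: all terms with penalisation, grouped terms, or the Charlson index. Name the time point too: protocol 6.4.4 collects comorbidities at diagnosis and at the study visit. If a summary term is chosen, state its power trade-off.
3. Report the odds ratio and 95% confidence interval from both models whatever the p-value, as tables 14.3.1.2 and 14.3.1.4 already imply.
4. Report each comorbidity's covariate-adjusted odds ratio for both outcomes as exploratory and state the count: 19 × 2 = 38.
5. Confirm that Crohn's disease and ulcerative colitis are pooled. Enter disease type or location, not both, because the location codes in SAP 5.3 (L1–L4, E1–E3) already determine the disease.

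Amend protocol 7.4 as well as 7.1, so that the all-comorbidities wording, the limit and the SAP model agree. If a predictive scale is still wanted, present any data-driven selection as a separate exploratory analysis.

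The cost is wording in two documents and no extra patients. Individual odds ratios will be imprecise, and the primary analysis will no longer be a data-driven model. False positives among the 38 exploratory estimates are not reduced (38 × 0.05 = 1.9 expected at the 5% level if none matters), but all of them will be visible.

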7.3. Secondary efficacy endpoints

- Secondary endpoint: Evaluate the impact of Extraintestinal Manifestations profile in IBD patients on treatment response to biological therapy.

The analysis that will be performed to answer the objective will be the following:

To evaluate the impact of extraintestinal manifestations profile in IBD patients on treatment response to biological therapy, a logistic regression analysis will be performed, in which **lack of response during the induction phase** will be used as the dependent variable and patient disease (CD or UC) and different extraintestinal manifestations variables (arthropathy and arthritis, metabolic bone disease, eye disease, oral, aural and nasal disease, skin disease, hepato-pancreato-biliary disease, neurological disease, cardiovascular manifestations of IBD,

pulmonary manifestations of IBD) will be used as independent variables, yielding the following results: Odds Ratio, 95%CI, p-value, sensitivity and specificity.

We will repeat this analysis with the **loss of response during the maintenance phase variable** as dependent variable.

- **Secondary endpoint: Describe the percentage of IBD patients exhibiting co-morbidities.**

The analysis that will be performed to answer the objective will be the following:

We will provide the frequencies, percentages and 95%CI of the following comorbidities for patients with Crohn's Disease and Ulcerative Colitis separately:

- Myocardial Infarction (yes/no).
- Congestive Heart Failure (yes/no).
- Peripheral Vascular Disease (yes/no).
- Cerebrovascular Disease (yes/no).
- Dementia (yes/no).
- Chronic Obstructive Pulmonary Disease (yes/no).
- Connective Tissue Disease (yes/no).
- Peptic Ulcer Disease (yes/no).
- Mild Chronic Hepatopathy (yes/no).
- Diabetes Mellitus (yes/no).
- Hemiplegic (yes/no).
- Moderate-Severe Chronic Kidney Disease (yes/no).
- Diabetes with lesions in target organs (yes/no).
- Solid Tumor (yes/no).
- Leukemia (yes/no).
- Lymphoma (yes/no).
- Moderate-Severe Chronic Hepatopathy (yes/no).
- Solid tumor with metastases (yes/no)
- Acquired immunodeficiency syndrome (AIDS) (yes/no).

- **Secondary endpoint: Determine the co-morbidities profile according to the level of IBD severity.**

The analysis that will be performed to answer the objective will be the following:

We will classify the patients into IBD severe or non-severe at baseline based on the HBI and PMI scores according the following criteria:

Harvey-Bradshaw Index score

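### The two primary logistic models select by Wald with no rule for separation, so a rare comorbidity whose carriers all share one outcome can pass the screen and then be dropped; in the three secondary models it would get an unbounded or zero odds ratio.

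*SAP*

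**What the plan says.** SAP 7.2 plans two primary logistic models, one for lack of response at induction and one for loss of response in maintenance. Both pool Crohn's disease and ulcerative colitis, with disease as a candidate covariate. The candidates include 19 single yes/no comorbidities, among them dementia, hemiplegia, leukemia, AIDS and metastatic tumor. A variable is carried forward if its univariable p-value is below 0.1, using chi-squared for categorical variables. Then: "The models will be assessed using stepwise automatic variable Wald entry (backward and forward) techniques". No entry or removal threshold is given for the stepwise part.

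SAP 7.3 adds three models. Two regress the same outcomes on nine extraintestinal manifestations plus disease. One regresses baseline severity on the comorbidities plus disease. Each is specified as "yielding the following results: Odds Ratio, 95%CI, p-value, sensitivity and specificity", with no screen and no selection rule.

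No estimator is named. Protocol 7.3 names SAS 9.1 or SPSS 19, and the logistic shell in SAP Appendix 1 has the layout of ordinary logistic output (step, df, Sig., Exp(B), 95% interval). No exact, penalised or profile-likelihood method appears, and no minimum number of carriers. The only size rule concerns outcome counts. Protocol 7.1 says "Considering a minimal sample of 10 patients that present the event of interest per independent variable included in the logistic regression model", and Protocol 7.4 caps the number of variables "to ensure a minimum of 10 patients per independent variable and response category in the dependent one". Fisher's exact test appears only for two-way comparisons (Protocol 7.3 and the COMP1 shell).

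**The concern.** When all carriers of an indicator have the same outcome, the likelihood keeps rising as the coefficient grows, so no finite estimate exists. The iterations stop at an arbitrary large coefficient with a standard error hundreds of times larger, and the Wald statistic is close to zero however strong the evidence. Two consecutive steps in SAP 7.2 then use the same data in opposite ways: the chi-squared screen admits the variable because the association is strong, and the Wald step discards it.

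These models are the planned answer to the primary objective, the impact of the comorbidity profile on response. A clear signal from a rare diagnosis could therefore be missing from the final model for purely numerical reasons. In the secondary models the same situation would put an odds ratio of the order of 10^9, or near zero, in the table with an interval that means nothing.

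**Working it through.** **1. The plan's own figure.** Protocol 7.1: "Response to treatment with biologics is estimated at 50%, meaning that half of included patients are expected to be non-responders", with "a maximum of 10 independent variables per model". Ten events × 10 variables / 0.5 = 200 per disease, which matches "a minimum estimated sample of 200 UC patients and 200 CD patients is required". Pooled, N = 400 with 200 events. The rule counts outcomes, not carriers: 5 carriers among 200 non-responders and 200 responders satisfy it and can still separate.

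**2. Which separated indicators pass the screen.** If k carriers all fail, with E events in N patients, Pearson χ² = N·k·(N−E) / [(N−k)·E]. At N=400 and E=200 this is 400k/(400−k):
- k=1: 1.00, p=0.317 (screened out)
- k=2: 2.01, p=0.156 (screened out)
- k=3: 3.02, p=0.082 (passes)
- k=5: 2000/395 = 5.06, p=0.024 (passes)

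Protocol 4 gives a lower rate: "up to 30% of patients do not respond to induction therapy (primary non-response". At 30% (E=120), k=1 fails the screen (p=0.126) and k=2 passes (p=0.030).

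**3. What the Wald step does.** Maximum likelihood stopped at 20 iterations, N=400, E=200, 5 of 5 failing: coefficient 21.23, odds ratio exp(21.23) ≈ 1.7×10^9, standard error 17,975. Then z = 21.23/17,975 = 0.0012 and p = 0.999. With the standard error from the preceding iteration, p is 0.998. The likelihood-ratio p on the same table is 0.008. At E=120 with 4 of 4 failing, Pearson p=0.002 and Wald p=0.999. Halving the sample changes nothing: N=200, E=100, 5 of 5 gives Pearson p=0.024 and Wald p=0.999.

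In 300 simulated data sets with disease, gender and time as covariates and 6 of 6 carriers failing, the median score p was 0.015 and the Wald p was at least 0.9989 in every run.

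**4. Firth on the same table.** For a 2×2 table the Firth estimate equals adding 0.5 to each cell: (5.5 × 200.5)/(0.5 × 195.5) = 11.3. The profile penalised 95% interval is 1.3 to about 1,480, and the penalised likelihood-ratio p is 0.026. The test matters: a Wald p on the Firth estimate is still 0.10 at 6 of 6.

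**5. How often, with no true effect.** The documents give no prevalences, so 0.5%, 1% and 2% are assumptions (2, 4 and 8 expected carriers in 400).

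*Primary models, 50% events:* P(all carriers fail, k≥3) = Σ over k≥3 of Binomial(400, π) × 0.5^k. At π=1% the sum over all k is 0.995^400 = 0.1347. Subtract k=0 (0.0180), k=1 (0.0363) and k=2 (0.0365) to get 0.044. At 0.5% and 2% the result is 0.030 and 0.014. Counting all-respond as well doubles these to 5.9%, 8.8% and 2.8%.

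*Secondary models, no screen, 50% events:* P(k≥1, all on one side) at 1% = 2 × (0.1347 − 0.0180) = 0.233. At 0.5% and 2% it is 0.47 and 0.035. The event rate of the severity model (HBI above 16, partial Mayo 8 to 9) is not given. If 15% were severe, the same sum with 0.15^k + 0.85^k gives 65%, 55% and 30%.

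**6. Without full separation** the failure is mild: 9 of 10 carriers failing gives an odds ratio of 9.4, Wald p=0.035 and chi-squared p=0.010.

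**The case against.** - **The signal is not lost from the report.** Tables 14.3.1.1 and 14.3.1.3 show every univariable comparison, and 5 of 5 would appear there at p=0.024. This stands, but those tables are unadjusted, and the adjusted models are the stated analysis of the primary objective.
- **Leaving a multivariable model after passing a univariable screen is normal.** It is, when adjustment explains the association. Here the variable leaves because the Wald statistic fails, with no covariate involved.
- **The screen protects against the sparsest cases.** At 50% events, 1 or 2 carriers never reach the primary models. If the analyst read Fisher's p from the COMP1 shell instead of Pearson's, 3 of 3 (0.248) and 4 of 4 (0.123) would also stop there, though 5 of 5 (0.061) would pass.
- **A carrier minimum does most of the work.** With a floor of 5 carriers, separation in either direction plus passing the screen falls to 0.3% to 1.4% at these prevalences. This stands under no effect. A true effect makes all-fail patterns more likely, and the Firth interval at 5 of 5 is very wide in any case.

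A reader might infer that all five models delete such comorbidities. The documents do not support this: Wald selection is written only in SAP 7.2, two of the other models contain extraintestinal manifestations instead of comorbidities, and the step column in the shared shell is layout, not a rule. A reader might also add the no-carrier cases and quote 60%, 25% and 4% as the chance that an indicator is unestimable. For the primary models that counts indicators the screen removes, and Firth cannot estimate an indicator with no carriers either.

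**Conclusion.** The gap is real and should be fixed. In the two primary models, an indicator that passes the chi-squared screen with all carriers on one side is dropped at a Wald p near 1, whatever usual removal threshold is used. In the three secondary models the result is an unbounded or zero odds ratio with a meaningless interval, not removal.

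The size for any one diagnosis is modest in the primary models (a few percent under no effect, more under a true effect). It is larger in the secondary models, where nothing filters one or two carriers.

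This rests on two assumptions: that the models are fitted by ordinary maximum likelihood, and that some of the listed diagnoses have prevalences around 2% or less. The conclusion that the models would be wrong for most diagnoses is not supported. The documents give no prevalences, and the lists include diabetes, chronic obstructive pulmonary disease, arthropathy and skin disease, which need not be rare in this population.

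**What to change.** - In SAP 7.2 and 7.3, fit the models by Firth penalised likelihood, with profile penalised-likelihood 95% intervals and penalised likelihood-ratio p-values.
- In SAP 7.2, do not use Wald p-values to remove comorbidities.
- State a minimum number of carriers (for example 5). Report indicators below it as counts by outcome, or within a grouped term.
- Amend the software sentence in Protocol 7.3 to name a procedure that fits penalised likelihood, and adapt the logistic regression shell to the new interval and p-value.

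The cost is SAP wording, one procedure and one shell, with no new data. The downside is that odds ratios are shrunk slightly towards 1 and intervals for rare diagnoses will be wide, which reflects how little information a few carriers hold.
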